Attachment 2: HIV-Risk Assessment

The following are intended as guidelines for the investigator to help identify potential vaccine trial participants at “low risk” for HIV infection in the US and Switzerland. Outside these countries, in addition to minimum requirements specified by the first two criteria defined below (“Have oral, vaginal or anal intercourse with an HIV-infected partner, or a partner who uses injection drugs” and “Give or receive money, drugs, gifts or services in exchange for oral, vaginal or anal sex”), low risk criteria as defined by local standards would be applicable.

HVTN Low Risk Guidelines
August 1, 2013

HIV VACCINE
TRIALS NETWORK

The following are intended as guidelines for the investigator to help identify potential vaccine trial participants at “low risk” for HIV infection in the US and Switzerland. These guidelines are based on behaviors within the last 6-12 months prior to enrollment; however, it may be appropriate to consider a person’s behavior over a longer period of time than specified to assess the person’s likelihood of maintaining low risk behavior. *Some volunteers may not be appropriate for enrollment even if they meet these guidelines.* These guidelines should be supplemented and interpreted with local epidemiologic information about HIV prevalence in your area and community networks. The investigator may review the risk level of any volunteer with the site PI and/or the Protocol Safety Review Team.

A volunteer may be appropriate for inclusion if he/she meets these guidelines:

1. SEXUAL BEHAVIORS

In the **last 12 months** did not:

- Have oral, vaginal or anal intercourse with an HIV-infected partner, or a partner who uses injection drugs
- Give or receive money, drugs, gifts or services in exchange for oral, vaginal or anal sex

AND

In the **last 6 months** has abstained from penile/anal or penile/vaginal intercourse, OR

In the **last 6 months**:

- Had 4 or fewer partners of the opposite birth sex for vaginal and/or anal intercourse, OR

Is an MSM (person born male with partner(s) born male) who, in the **last 12 months**:

- Had 2 or fewer MSM partners for anal intercourse and had no unprotected anal sex with MSM, OR
- Had unprotected anal intercourse with only 1 MSM partner, within a monogamous relationship lasting at least 12 months (during which neither partner had any other

partners). If the monogamous relationship ended, the volunteer may then have had protected anal intercourse with 1 other MSM partner (total 2 or fewer partners in the last 12 months).

Is a transgender person, regardless of the point on the transition spectrum, having sex with men (born male) and/or other transgender persons, who **in the last 12 months**:

- Had 2 or fewer partners for anal or vaginal intercourse, and had no unprotected anal or vaginal sex, OR
- Had unprotected anal or vaginal intercourse sex with 1 partner only within a monogamous relationship lasting at least 12 months (during which neither partner had any other partners). If the monogamous relationship ended, may then have had protected anal or vaginal sex with 1 other partner (total 2 or fewer partners in the last 12 months).

AND

Uses or intends to use condoms in situations which may include penile/anal or penile/vaginal intercourse with new partners of unknown HIV status, occasional partners, partners outside a primary relationship, and/or partners known to have other partners.

2. NON-SEXUAL BEHAVIORS

In the **last 12 months** did not:

- Inject drugs or other substances without a prescription
- Use cocaine, methamphetamine, or excessive alcohol, which in the investigator's judgment, rendered the participant at greater than low risk for acquiring HIV infection.

The investigator's judgment should consider local epidemiologic information about HIV prevalence in the area and community networks.

A volunteer is NOT appropriate for inclusion if he/she:

Acquired an STI (ie, new infection) in the last 12 months:

- Syphilis
- Gonorrhea
- Non-gonococcal urethritis
- HSV-2
- Chlamydia
- Pelvic inflammatory disease (PID)
- Trichomonas
- Mucopurulent cervicitis
- Epididymitis
- Proctitis
- Lymphogranuloma venereum
- Chancroid
- Hepatitis B

Attachment 3: Test of Understanding^o

Please read each question and answer whether the statement is **True or False**.

| | | |
|----------------------------------|-----------------------------------|--|
| True  | False  | 1. The vaccines you will receive in this study protect against HIV. |
| True  | False  | 2. You will need to come to the clinic for 18 scheduled visits over the next year. |
| True  | False  | 3. The vaccines in this study can give you HIV. |
| True  | False  | 4. One purpose of this study is to determine if these vaccines are safe to administer to humans. |
| True  | False  | 5. Participants in this study will need to avoid engaging in activities that may expose them to HIV infection. |
| True  | False  | 6. You may take other experimental (test) products while you are taking part in this study. |
| True  | False  | 7. You may withdraw from the study at any time if you choose or your participation may be stopped if the study team decides it is in your best interest. |
| True  | False  | 8. Women participating in this study are permitted to become pregnant during the study. |
| True  | False  | 9. A participant in this study may experience side effects after vaccination. |
| True  | False  | 10. Some participants in this study may develop a positive HIV test result, despite the fact that they are not HIV infected.. |

^o Adaptations to the TOU are allowed for local purposes, after IRB and sponsor approval.

Attachment 4: Social Impact Questionnaire**Vaccine Research Center (VRC) Social Impact Case Report Form ¹⁹**

| | Social Impact Question | Yes or No | If Yes, did you consider this to be harmful to you? |
|--|---|--|--|
| 1. Personal Relationships | Did you have problems with family, friends, significant others or sex partners because of participation in this clinical trial? |  Yes  No |  Yes  No |
| | Comment:  resolved;  continuing | |  mild;  moderate;  major |
| 2. Travel or Immigration | Did you have problems getting legal permission to travel to or from another country, such as being denied a visa, or having problems with immigration/naturalization because of participation in this clinical trial? |  Yes  No |  Yes  No |
| | Comment:  resolved;  continuing | |  mild;  moderate;  major |
| 3. Employment | Have you been turned down for a new job, lost a job, or had other problems at work because of participation in this clinical trial? |  Yes  No |  Yes  No |
| | Comment:  resolved;  continuing | |  mild;  moderate;  major |
| 4. Education | Have you been turned down by an educational program, told to leave an educational program, or had other problems at school because of participation in this clinical trial? |  Yes  No |  Yes  No |
| | Comment:  resolved;  continuing | |  mild;  moderate;  major |
| 5. Medical or Dental | Have you been refused medical or dental care or treated negatively by a health care provider because of participation in this clinical trial? |  Yes  No |  Yes  No |
| | Comment:  resolved;  continuing | |  mild;  moderate;  major |
| 6. Health Insurance | Have you lost health insurance, had a problem getting new health insurance, or had other problems related to health insurance because of participation in this clinical trial? |  Yes  No |  Yes  No |
| | Comment:  resolved;  continuing | |  mild;  moderate;  major |
| 7. Life Insurance | Have you lost life insurance, had a problem getting new life insurance, or had other problems related to life insurance because of participation in this clinical trial? |  Yes  No |  Yes  No |
| | Comment:  resolved;  continuing | |  mild;  moderate;  major |
| 8. Housing | Have you had trouble getting or keeping housing, or had other problems related to housing because of participation in this clinical trial? |  Yes  No |  Yes  No |
| | Comment:  resolved;  continuing | |  mild;  moderate;  major |
| 9. Military/Other Government Agency | Have you had a problem with the military or any other government agency because of participation in this clinical trial? |  Yes  No |  Yes  No |
| | Comment:  resolved;  continuing | |  mild;  moderate;  major |
| 10. Other | Have you had any other problem not covered by the other questions because of anything related to participation in this clinical trial? |  Yes  No |  Yes  No |
| | Comment:  resolved;  continuing | |  mild;  moderate;  major |

INVESTIGATOR AGREEMENT

I have read this protocol and agree that it contains all necessary details for carrying out this study. I will conduct the study as outlined herein and will complete the study within the time designated.

Scheduled visits that cannot be conducted in person at the study site will be performed to the extent possible as a remote visit, a home visit, or delayed until such time that on-site visits can be resumed.^a At each contact, participants will be interviewed to collect safety data. Key endpoint assessments should be performed if required and as feasible. Participants will also be questioned regarding general health status to fulfill any physical examination requirement.

Every effort should be made to adhere to protocol-specified assessments. Modifications to protocol-required assessments may be permitted via COVID-19 Appendix after consultation with the participant, investigator, and the sponsor. Missed assessments/visits will be captured in the clinical trial management system for protocol deviations. Discontinuations of study interventions and withdrawal from the study should be documented with the prefix “COVID-19-related” in the case report form (CRF). Any deviations to study procedures occurring due to the COVID-19 pandemic need to be properly captured in the clinical trial management system (or CRF), with the prefix “COVID-19-related” (including actual visit date) and will be summarized in the clinical study report.

The sponsor will continue to monitor the conduct and progress of the clinical study, and any changes will be communicated to the sites and to the health authorities according to applicable guidance documents and regulations. Modifications made to the study conduct as a result of the COVID-19 pandemic will be summarized in the clinical study report.

^a An on-site visit is defined as a visit during which the participant and the qualified site staff are both present in person at the study site.

A remote visit is defined as a visit during which there is no direct in-person physical presence between the participant and the qualified site staff (telephone or video call).

A home visit is defined as a visit during which the participant and the qualified site staff are both present at the participants’ home.

GUIDANCE SPECIFIC TO THIS PROTOCOL

The following emergency provisions are meant to ensure participant safety on study while site capabilities are compromised by COVID-19 related restrictions. When restrictions are lifted, sites should revert to the original protocol conduct as soon as feasible and in accordance with local guidance and regulations and in agreement with the institutions and the investigator's assessment of the safety of site staff and study participants.

Study Visits and Assessments:

- When site visits are not possible, sites should collect the assessments via remote visits, or via home visits (if possible and if the participant allows and provides consent to it). The actual visit date and the type of visit (i.e., remote or home visit) should be captured in the eCRF according to the eCRF completion guidelines.
- Procedures that can't be performed in case of remote visits (e.g., blood sampling for immunogenicity and HIV testing), should be documented as protocol deviations and labelled as "missed due to COVID-19". The protocol deviations need to be captured in the source document.

Informed Consent

- Consenting and re-consenting of participants for the measures taken (including also remote consenting by phone or video consultation) will be performed as applicable and according to local guidance for informed consent applicable during the COVID-19 pandemic. The process is to be documented in the source documents.

Source Data Verification/Monitoring

- In case on-site monitoring visits are not possible, the site monitor may contact the investigator to arrange monitoring visits and activities remotely (in accordance with site and local requirements). Additional on-site monitoring visits may be needed in the future to catch up on source data verification.

Site Audits

- During the COVID-19 pandemic and at the impacted sites, study site GCP audits with direct impact/engagement from the investigator and study site personnel may not be conducted in order to comply with national, local, and/or organizational social distancing restrictions. Additional quality assurance activities such as remote audits or focused review of study related documents may take place with limited impact/engagement if possible.

INVESTIGATOR AGREEMENT

COVID-19 Appendix

JNJ-55471468, JNJ-55471494, JNJ-55471520, JNJ-55471533, JNJ-55471572, JNJ55471585

Clinical Protocol HIV-V-A004

INVESTIGATOR AGREEMENT

**AMENDMENT HISTORY**

V1.0 15 May 2018	First version
V2.0 22 April 2022	Updated version to include long term extension data up to week 336

**ABBREVIATIONS**

ADCP	antibody dependent cellular phagocytosis
AE	adverse event
ALT	alanine aminotransferase
ANC	absolute neutrophil count
AST	aspartate aminotransferase
BAMA	binding antibody multiplex assay
BIDMC	Beth Israel Deaconess Medical Center
BMI	body mass index
CRF	case report form
CTP	clinical trial protocol
DAIDS	Division of AIDS
DP	drug product
dTA	data transfer agreement
EDC	electronic data capture
ELISA	enzyme-linked immunosorbent assay
ELISPOT	Enzyme-Linked ImmunoSpot
ENV	envelope
FHCRC	Fred Hutchinson Cancer Research Center
GCP	Good Clinical Practice
HD	high dose
HIV	human immunodeficiency virus
ICS	intracellular cytokine staining
IG	immunogenicity
LD	low dose
LLOQ	lower limit of quantification
LOD	limit of detection
LTE	long term extension
SAE	serious adverse event
ULN	upper limit of normal
VISP	vaccine induced seropositivity
VISR	vaccine induced seroreactivity
VRC	Vaccine Research Center
WBC	white blood cell

**DEFINITION OF TERMS**

Randomization	1:1:1:1:1:1 ratio																																								
Study vaccine	
 
- Ad26.Mos.HIV (Ad26.Mos.1.Env + Ad26.Mos1.Gag-Pol + Ad26.Mos2.Gag-Pol): Total dose is <math>5 \times 10^{10}</math> viral particles (vp) per 0.5 mL injection
 
- MVA-Mosaic (MVA-Mosaic1 + MVA-Mosaic2): Total dose is <math>10^8</math> plaque-forming units (pfu) per 0.5 mL injection
 
- gp140 DP: 
 
- Low-dose: gp140 DP with 50 mcg total protein, mixed with aluminum phosphate adjuvant (0.425 mg aluminum) at the pharmacy, per 0.5 mL injection
 
- High-dose: gp140 DP with 250 mcg total protein, mixed with aluminum phosphate adjuvant (0.425 mg aluminum) at the pharmacy, per 0.5 mL injection
 
 
 
- Placebo: 0.9% saline, 0.5 mL injection
 
																																								
Vaccination compliance	Each vaccine administered (if applicable) according to planned schedule																																								
Vaccine regimen	
  
 Group	Planned N	Day 1, Week 12	Week 24, Week 48	
   
 1	50	Ad26.Mos.HIV	Ad26.Mos.HIV + gp140 (250mcg+adjuvant)	
 
 2	50	Ad26.Mos.HIV	Ad26.Mos.HIV + gp140 (50mcg+adjuvant)	
 
 3	50	Ad26.Mos.HIV	Ad26.Mos.HIV + Placebo	
 
 4	50	Ad26.Mos.HIV	MVA-Mosaic + gp140 (250mcg+adjuvant)	
 
 5	50	Ad26.Mos.HIV	MVA-Mosaic + gp140 (50mcg+adjuvant)	
 
 6	50	Ad26.Mos.HIV	MVA-Mosaic + Placebo	
 
 7	50	Ad26.Mos.HIV	gp140 (250mcg+adjuvant) + Placebo	
 
 8	50	Placebo	Placebo + Placebo	
  
	Group	Planned N	Day 1, Week 12	Week 24, Week 48	1	50	Ad26.Mos.HIV	Ad26.Mos.HIV + gp140 (250mcg+adjuvant)	2	50	Ad26.Mos.HIV	Ad26.Mos.HIV + gp140 (50mcg+adjuvant)	3	50	Ad26.Mos.HIV	Ad26.Mos.HIV + Placebo	4	50	Ad26.Mos.HIV	MVA-Mosaic + gp140 (250mcg+adjuvant)	5	50	Ad26.Mos.HIV	MVA-Mosaic + gp140 (50mcg+adjuvant)	6	50	Ad26.Mos.HIV	MVA-Mosaic + Placebo	7	50	Ad26.Mos.HIV	gp140 (250mcg+adjuvant) + Placebo	8	50	Placebo	Placebo + Placebo	Group	Planned N	Day 1, Week 12	Week 24, Week 48
Group	Planned N	Day 1, Week 12	Week 24, Week 48																																						
1	50	Ad26.Mos.HIV	Ad26.Mos.HIV + gp140 (250mcg+adjuvant)																																						
2	50	Ad26.Mos.HIV	Ad26.Mos.HIV + gp140 (50mcg+adjuvant)																																						
3	50	Ad26.Mos.HIV	Ad26.Mos.HIV + Placebo																																						
4	50	Ad26.Mos.HIV	MVA-Mosaic + gp140 (250mcg+adjuvant)																																						
5	50	Ad26.Mos.HIV	MVA-Mosaic + gp140 (50mcg+adjuvant)																																						
6	50	Ad26.Mos.HIV	MVA-Mosaic + Placebo																																						
7	50	Ad26.Mos.HIV	gp140 (250mcg+adjuvant) + Placebo																																						
8	50	Placebo	Placebo + Placebo																																						

## 1. INTRODUCTION

This statistical analysis plan (SAP) was initially written to describe the analyses of the main part of the study (up to Week 96). This updated version covers also the reporting of data collected till the end of the long term extension (LTE) which lasted up to Week 336 only for group 1 and 2 (final analysis at end of study). At the time this SAP was written the Week 96 statistical analysis was already performed and will not be rerun. The below described analyses will be performed on fully unblinded data.

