2. OBJECTIVES AND HYPOTHESIS

2.1. Objectives

Primary Objectives

The primary objectives are:

- To assess the safety/tolerability of various prime/boost regimens containing Ad26.Mos.HIV, MVA-Mosaic, and/or gp140 DP components.
- To compare Env binding antibody responses between the different vaccine regimens.

Secondary Objective

The secondary objective is:

- To assess other antibody binding, antibody effector function and antibody characterization, and cellular responses.

Exploratory Objectives

The exploratory objectives are:

- To explore immune responses to the different vaccine regimens in mucosal secretions in a subset of subjects.
- To explore gene expression patterns between the different vaccine regimens.
- To explore neutralization antibodies against the Ad26 vector.
- To assess the social impact of participation in an HIV vaccine study for subjects via a social impact questionnaire.
- To explore durability of the vaccine regimen in the groups selected for the long-term extension phase.

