### 2.3.1. LTE Analysis Set

The Long Term Extension (LTE) population consists of all subjects in the Per-Protocol Immunogenicity Analysis Set, randomized in group 1 or 2 who had at least one visits in the long term extension part of the study.

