## 6. IMMUNOGENICITY

### 6.1. Analysis specifications

The analysis of immunogenicity will be done on the PPI analysis set (Section 2.3).

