#### Humoral assays

For all the humoral assays the immune response values will be  $\log_{10}$ -transformed before any further handling. The  $\log_{10}$ -transformed values will be used throughout the analysis. In the graphs, original values will be displayed on the  $\log_{10}$  scale.

For each assay and at each time point geometric mean of actual values, geometric mean increases and percentage of responders, all with corresponding 95% CIs will be provided in the tables. The definition of responders is defined in

section 6.4. for each assay. Graphical presentations will be provided displaying dots for the subject values and including the geometric mean and the percentage of responders. If available, baseline values will be summarized pooling the 8 groups and will be displayed on the left of each graph. Week 28 and Week 52 timepoints will be plotted next to each other for each group, a line will link the geometric mean (or the median) of the 2 different time points within the same group.

In the graphs the actual values will be shown and the LLOQ cut-off will be visualized, the values below LLOQ or below LOD will be visualized with the value imputed as described in section 6.3.

Vaccine durability will be shown by linear plots of the GM/median for each group.

Reverse distribution curves of the actual values will be provided for selected assays.

For BAMA the median will be reported instead of the geometric mean. Cumulative number of responses across the IgG/antigen classes will be tabulated.

Magnitude-breadth (MB) plots for the BAMA assay will be provided at each timepoint to explore the magnitude (MFI of IgG3 and of IgG breadth binding antibodies) and breadth (number antigens at a given MFI) of each individual serum sample assayed. MB curves will show, for each possible MFI threshold, the fraction of antigens with MFI greater than this threshold.

The group-specific curve obtained as the average MB across all subjects in that group will be displayed. The AUC-MB is calculated as the average of the MFI over the panel of antigens.

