#### **6.4. Handling of Missing and/or Invalid Immune Response Data**

Analysis will be carried out on the available data, no imputation will be done for missing samples.

BAMA and ICS unreliable values should be excluded from the analysis: those records will be flagged in the SDTM dataset.

LLOQs by assay/test are listed in Table 1. Values below LLOQ or LOD will be handled as follows:

- Calculation of Geomean (humoral response) and median (cellular response):
  - o values < LLOQ are imputed =LLOQ/2
  - o values = LOD are not imputed unless no LLOQ is available. In that case LOD will handled similarly to LLOQ (see ADCP)
- Calculation of fold increases from baseline:
  - o values <LLOQ are imputed =LLOQ
  - o values =LOD are imputed = LLOQ when LLOQ is available

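### The planned long-term extension durability outputs do not separate waning from changes in who is sampled; a common-cohort display and within-subject ratios would largely do so

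*SAP*

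**What the plan says.** Protocol 2.1 lists among the exploratory objectives "To explore durability of the vaccine regimen in the groups selected for the long-term extension phase". Protocol 9.1.8 offers the extension to Group 1 and 2 subjects who received all four vaccinations, under a separate consent. The schedule has ten visits, from Week 120 to Week 336.

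The SAP handles this as follows:

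- **Sets.** The LTE Analysis Set is made up of per-protocol immunogenicity (PPI) subjects "randomized in group 1 or 2 who had at least one visits in the long term extension part of the study". Section 6.1 names a different set: "The analysis of immunogenicity will be done on the PPI analysis set". No section assigns the LTE set to an immunogenicity output.
- **Durability display.** Section 6.3 (Humoral assays) says "Vaccine durability will be shown by linear plots of the GM/median for each group". The end of 6.3 applies the same approaches to extension timepoints.
- **Missing samples.** Section 6.4 says "Analysis will be carried out on the available data, no imputation will be done for missing samples".
- **Change measure.** The only one, in 6.3 to 6.5, is the increase from Week 0.
- **Earlier analysis.** The Introduction says "At the time this SAP was written the Week 96 statistical analysis was already performed and will not be rerun".
- **Retention.** Section 4.2 tabulates the number and percentage of subjects at each extension visit, but not against titre.

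**The concern.** A line through group means describes waning only if the same people, or an equivalent sample of them, stand behind each point. Here the composition can change at least twice. It can change at Week 96, because entry needs fresh consent. It can change again at every extension visit, because one attendance is enough for the LTE set and missed samples are simply absent. The COVID-19 Appendix adds a further route to missing samples, since blood cannot be drawn at a remote visit.

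A flat line after Week 96 could then mean that antibody persists, or that higher responders kept attending. A step between Week 96 and Week 120 could be a change in who was sampled.

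Fold increase from Week 0 does not settle this. It measures response over baseline, not retention from peak. Where baseline is below the LLOQ, SAP 6.5 defines it as value divided by LLOQ, so it carries the same shift in composition.

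The curve will be read. Protocol 3.1 says that Groups 1 and 2 form the basis for regimens to be taken into future studies.

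**Working it through.** **Inputs.** From Protocol 11.2: SD 0.6 on log10, 45 evaluable per group, two-sided 5%, 80% power, 2.3-fold detectable difference. The documents give no extension retention, no link between attendance and titre, and no within-subject correlation. These are assumed below and shown over a range.

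**The plan's own figure.** Detectable difference = (1.96 + 0.842) × 0.6 × √(2/45) = 0.354 log10, or 2.26-fold. This agrees with the stated 2.3-fold, so the SD is used as given.

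**Shift from selective attendance.** Let a proportion p give a sample, and let the propensity to attend correlate ρ with log10 titre. Under a normal selection model the mean of those retained moves by ρ × 0.6 × φ(z_p)/p on log10.

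| Retained p | ρ | Shift (log10) | Fold shift in GM |
|---|---|---|---|
| any | 0 | 0 | 1.00 |
| 0.7 | 0.1 | 0.1 × 0.6 × 0.348/0.7 = 0.030 | 1.07 |
| 0.5 | 0.2 | 0.2 × 0.6 × 0.399/0.5 = 0.096 | 1.25 |
| 0.4 | 0.3 | 0.3 × 0.6 × 0.386/0.4 = 0.174 | 1.49 |

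These are shifts at the visit whose titre drives attendance. If that is Week 52 and the within-subject correlation to an extension visit is 0.7, the shift at the extension visit is 0.7 times as large on log10: 0.021, 0.067 and 0.122, or 1.05-, 1.17- and 1.32-fold. The sign of ρ is also assumed; a negative ρ gives the same sizes in the other direction.

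**Effect on the reading.** Take true waning of 2.0-fold (0.301 log10), within-subject correlation 0.8 and attendance tied to Week 96 titre with ρ = 0.3. The selection shift s is 0.063 log10 at 80% retained and 0.116 at 60%.

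- Everyone at Week 96 against attenders later: 0.301 − 0.8s gives 1.78-fold at 80% and 1.62-fold at 60%.
- Attenders at both times: 0.301 + 0.2s gives 2.06-fold and 2.11-fold.

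A simulation of 20,000 runs with 45 subjects gave the same four values. With ρ = 0 and 80% retained, both readings gave 2.00. The common cohort removes the composition shift. It leaves a small error towards more waning, which is regression to the mean.

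**Precision.** Assume 25 extension samples nested in 45 at Week 52, with within-subject correlation 0.7.

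- Ratio of the two group means: SE = 0.6 × √(1/45 + 1/25 − 2 × 0.7/45) = 0.106, so the 95% margin is ×/÷ 1.61.
- Paired ratio in the 25: SE = 0.6 × √(2 × 0.3/25) = 0.093, so the margin is ×/÷ 1.52.

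Pairing gains little precision. Its main value is less composition bias.

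**The case against.** The strongest reply is that much of the alarm comes from inference. A reader might infer from the Introduction that the PPI curve to Week 96 will be spliced onto means of extension attenders, and that no Week 52 or Week 96 value will be produced for the LTE subjects themselves. The documents do not say so. Leaving the completed analysis alone does not prevent the extension report from re-summarising earlier visits for the LTE set, and a note to SAP Table 3, on phases and periods, says extension data are reported separately. What stands is that the SAP does not say which set supplies the earlier points. If the extension visits are shown alone, the same people have no peak or Week 96 anchor.

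A reader might also infer that waning and attendance can never be told apart. That is true only of the planned outputs: individual Week 52, 78 and 96 values exist.

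Other parts of the reply are correct:

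- The four-dose rule adds little difference from Week 52, because SAP 2.3.2 already drops later samples without an in-window fourth dose.
- The COVID-19 Appendix also allows home and delayed visits, so lost samples are possible but not established.
- Treating the 45 and the 25 as independent would give 0.6 × √(1/45 + 1/25) = 0.150, or ×/÷ 1.96. That overstates the imprecision because the samples are nested.
- No mechanism linking attendance to titre is documented.
- The objective is exploratory, and no hypothesis or Group 1 versus Group 2 durability test is planned.

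**Conclusion.** The point holds as a worthwhile, inexpensive improvement to an exploratory analysis. It does not touch the Week 28 primary analysis or the completed Week 96 analysis. As written, the durability output is a series of group summaries on available samples. Its membership can change after Week 96 and between extension visits, and no within-person measure of retention is planned.

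The size is uncertain. There is no shift if attendance is unrelated to titre, and about 1.07- to 1.49-fold over the assumed range. The shift is smaller at the extension visit (1.05- to 1.32-fold) if attendance acts through Week 52 titre with correlation 0.7. All of this rests on the protocol SD and on assumed retention and correlations. The documents support neither a claim that the curves will be joined nor a claim that the bias is present.

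**What to change.** In SAP 6.3, add for the LTE analysis set:

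1. On the durability plot, show the visits before the extension recalculated for LTE subjects alongside the extension visits, with n at each visit.
2. For each extension visit and by group, report the within-subject geometric mean ratio (median ratio where the assay is summarised by medians), with 95% CI, to two references. One is the assay's post-dose-4 visit: Week 52 for ELISA, Week 50 for ELISpot. The other is Week 96. Make these ratios the main durability summary.
3. State that the ratios reduce selection effects but do not fully remove them, because of regression to the mean.

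The cost is SAP wording and a few extra tables from data already collected, with no new samples and no rerun of the Week 96 analysis. The downside is that the durability plot rests on fewer subjects before Week 96.
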